6.4 Pregnancy

Investigators shall counsel male subjects who are sexually active with WOCBP on the importance of pregnancy prevention and the implications of an unexpected pregnancy. At a minimum, contraceptive counseling should be provided at the time of assent or consent. Investigators shall advise male subjects who are sexually active with WOCBP on the use of highly effective methods of contraception in non-pregnant partner, and on the use of condom in subjects with a pregnant partner, during treatment period and for 140 days following the last dose. Highly effective methods of contraception have a failure rate of <1% when used consistently and correctly. Pregnancy that occurs in a female partner of a male study participant should be reported to Roche.

HIGHLY EFFECTIVE METHODS OF CONTRACEPTION

- Hormonal methods of contraception including combined oral contraceptive pills, vaginal ring, injectables, implants and intrauterine devices (IUDs) such as Mirena® by the male subject's WOCBP partner. Female partners of male subjects participating in the study may use hormone-based contraceptives as one of the acceptable methods of contraception since they will not be receiving study drug.
- Non-hormonal IUDs, such as ParaGard®
- Complete abstinence

Complete abstinence is defined as complete avoidance of heterosexual intercourse and is an acceptable form of contraception for all study drugs. Subjects who choose complete abstinence are not required to use a second method of contraception, but female subjects must continue to have pregnancy tests. Acceptable alternate methods of highly effective contraception must be discussed in the event that the subject chooses to forego complete abstinence.

LESS EFFECTIVE METHODS OF CONTRACEPTION

- Diaphragm with spermicide
- Cervical cap with spermicide
- Vaginal sponge
- Male condom with or without spermicide
- Progestin only pills or male subject's WOCBP partner female condom*

* A male and female condom must not be used together.

6.5 Overdose

An overdose is defined as the accidental or intentional administration of any dose of a product that is considered both excessive and medically important. All occurrences of overdose must be reported as SAEs (see [Section 6.1.1](#) for reporting details).

6.6 Other Safety Considerations

Any significant worsening noted during interim or final physical examinations, electrocardiogram, x-ray filming, or any other potential safety assessment required or not

required by protocol should also be recorded as a non-serious or serious AE, as appropriate, and reported accordingly.

7 DATA MONITORING COMMITTEE AND OTHER EXTERNAL COMMITTEES

There will be a data monitoring committee (DMC) for this study. The DMC scope, frequency of review, membership, activities and other specifications are detailed in the DMC charter.

The DMC shall have access to partially unblinded data (coded treatment assignments), including but not limited to following: the frequency and spectrum of SAEs; Grades 3 and 4 laboratory abnormalities; occurrence of malignancies; and other select adverse events of interest. The DMC shall also review aggregate data results from the IAs. The DMC shall have the right to request full unblinding of the data (codes will be decoded to reveal actual treatment assignments). The DMC shall act as an advisor to the Sponsor and have responsibility for safeguarding the subjects' interests. The DMC shall bring any safety concerns to the attention of the Sponsor so that the Sponsor can review the data and prepare appropriate communications to the regulatory authorities.

8 STATISTICAL CONSIDERATIONS

8.1 Sample Size Determination

The total number of subjects of the study will be approximately 40, which consists of 3 dose panels of approximately 8 subjects each and an Expansion Panel of approximately 16 subjects. In each dose panel, subjects will be randomized 3:1 to either RO7239361 or placebo. Subjects who discontinue participation in the study prematurely may be replaced only if the reason for discontinuation is not related to study drug. For safety evaluation, the administration of RO7239361 to 6 subjects provides an 80% probability of observing at least one occurrence of any adverse event that would occur with 24% incidence in the population from which the sample is drawn.

8.2 Populations for Analyses

- Enrolled subjects: all consented subjects who entered screening
- Treated subjects: all subjects who received at least one dose of study drug or placebo

The *PK* data set includes all available concentration time data from the subjects who receive any RO7239361 medication. Additionally, all available derived PK parameter values will be included in the PK data set and reported, but only subjects with adequate PK profiles will be included in the summary statistics and statistical analysis.

The *PD* data set includes all available data from subjects for whom *PD* measurements are available at baseline and at least one other timepoint.

Subjects who receive placebo in any panel will be pooled into a single placebo group.

8.3 Endpoints

8.3.1 Primary Endpoint(s)

The primary objective is to assess safety and tolerability of multiple SC doses of RO7239361 in DMD boys. Primary endpoints are incidence of AEs, SAEs, AEs leading to discontinuation, and death, as well as marked treatment emergent abnormalities in clinical laboratory tests, vital sign measurements, ECGs, echocardiograms, and physical examinations across treatment conditions during the double-blind and *OL* phases of treatment.

8.3.2 Secondary Endpoint(s)

The first secondary objective to evaluate the PK of multiple SC doses of RO7239361 will be assessed using serum concentrations of RO7239361 at specified timepoints and will be measured by the following secondary endpoints:

- RO7239361 trough concentrations at Days 8, 15, 22, 29, Week 12, and Week 24
- Observed C_{max} of RO7239361 in the 1-week dosing interval following the doses on Day 1 and Day 29

The second secondary objective to evaluate the immunogenicity of multiple SC doses of RO7239361 will be measured by the assessment of immunogenicity samples for presence and titer of ADAs at the timepoints specified in [Table 5.1-1](#) through [Table 5.1-4](#). The following endpoints will be measured:

- Frequency of subjects with positive ADA assessment
- Frequency of subjects who develop positive ADA following a negative baseline
- Anti-RO7239361 antibodies on selected days

The third secondary objective to evaluate the effects of RO7239361 on free myostatin and myostatin-drug complex levels of RO7239361 will be measured by serum concentrations of free myostatin and myostatin-drug complex at the timepoints specified in [Table 5.1-3](#). The following endpoints will be measured:

- Serum concentration of free myostatin and drug-myostatin complex, percent inhibition of free myostatin at trough

The fourth secondary objective is to evaluate right thigh muscle changes through MRI measurements. The secondary endpoints that will be measured are absolute changes and percentage changes from baseline of CSA_{max} and fold number changes in contractile versus non-contractile content for muscles in the right thigh during the 24-week double-blind treatment period, compared to placebo.

8.3.3 *Exploratory Endpoint(s)*

The PD effects of multiple doses of RO7239361 in DMD boys will be evaluated by the following exploratory endpoints:

- Measures of function, including TFTs (4SC, 4SD, 10-m walk/run, *standing* from supine), 6MWD, and the NSAA)
- Serum analytes that may include but are not limited to:
 - miR-206, miR-133a, miR-1, miR-6 (control miR), miR-21 and miR-39
 - TGF- β concentrations which are associated with fibrosis of muscle seen in DMD
 - Follistatin
 - Creatine kinase concentrations and CK-MM, which are associated with muscle atrophy in DMD
- Urine analytes that include but are not limited to:
 - Titin protein amino-terminal fragment concentrations that are associated with muscle damage
- Upper and lower extremity strength obtained by manual myometry
- Ankle range of motion in degrees
- DXA measures of total lean body mass, fat mass and bone mineral density
- MRS measures of right thigh lipid fraction
- Health-related quality of life as measured by the PODCI
- Measures of pulmonary function, including FVC, FEV₁, MEP, MIP, CPF, and PFR
- Genetic variation status of genes suspected to modify DMD disease expression (including but not limited to LTBP4, SPP1)
- PUL measure of upper extremity motor function

8.4 *Analyses*

8.4.1 *Demographics and Baseline Characteristics*

Frequency distributions of gender and race will be tabulated. Summary statistics for age, body weight, height, and body mass index (BMI) will be tabulated.

8.4.2 *Efficacy Analyses*

Exploratory efficacy endpoints including but not limited to TFT (4SC, 4SD, 10-m walk/run, *standing* from supine), 6MWD, NSAA and PFTs will be tabulated by dose and study day; and the corresponding changes from baseline and percent change from baseline will be calculated and summarized.

8.4.3 *Safety Analyses*

All recorded AEs will be listed and tabulated by system organ class, preferred term and treatment. Vital signs and clinical laboratory test results will be listed and summarized by treatment. Treatment emergent laboratory abnormalities will be listed by toxicity grade (according to the NCI CTCAE, Version 4.0) and summarized by treatment. Any significant

physical examination findings will be listed. Echocardiogram and ECG readings will be evaluated by the central cardiac site and abnormalities, if present, will be listed. Values for ECG, vital signs and clinical laboratory test results outside the pre-specified criteria will also be listed and summarized. ECG readings will be evaluated by the investigator and abnormalities, if present, will be listed. The placebo data will be pooled as one group.

Summary statistics will be presented for each echocardiogram/ECG/VS parameter and the corresponding changes from baseline by treatment and timepoint. Plots of mean change from baseline value for each parameter versus time since dosing will be presented by treatment. The last pre-dose value is defined as baseline value.

8.4.4 Pharmacokinetic Analyses

Serum RO7239361 concentrations will be summarized by treatment group, study day and times postdose. To assess the attainment of steady state, geometric mean C_{trough} values will be plotted versus study day.

Dose proportionality of RO7239361 will be assessed by estimating the slope of the linear regression of the natural log of the PK parameter (C_{max} and C_{trough}) on the natural log of dose (by tiered body weight) using the power model described by Gough et al.³² Descriptive summary statistics, including means, standard deviations, coefficients of variation, minima, medians, and maxima will be provided for serum RO7239361 concentrations at different timepoints.

PK and target engagement data collected in this study may be used to develop a population PK/PD model to estimate model-derived population and individual PK/PD parameter (e.g., CL/F, Vc/F, Ka, etc.) and may be reported separately from the clinical study report.

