1.6.4.1 Pharmacokinetics of RO7239361

RO7239361 achieves peak concentrations *in serum* between 3 and 5 days post-injection and has a terminal half-life of approximately 7 to 10 days across all doses following single SC dose administration (5, 15, 45, 90, and 180 mg). The increase in exposure with dose of RO7239361 appeared to be generally proportional up to 90 mg but was greater than proportional at the highest dose of 180 mg (Study CN001001).

Following multiple RO7239361 administration, T_{max} of RO7239361 was achieved approximately 2–3 days after dosing. The half-life estimates following the last dose were from 10 to 13 days. PK parameters increased in a slightly greater than proportional manner over the explored dose range (15 mg Q1W to 180 mg Q1W) (Study CN001001).

In the current 226 study, the pharmacokinetics of RO7239361 in ambulatory boys with DMD were analyzed using a population-PK approach. The pharmacokinetics of RO7239361 were well characterized using a PD/PK model based on the target-mediated drug disposition concept, and body weight was found to be the only covariate. Steady state was reached after ~12 weeks of Q1W administration. The pharmacokinetics of RO7239361 appear to be dose proportional, considering the between-subject variability. T_{max} of RO7239361 was achieved within 24–30 hours after dosing.

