Subjects will receive SC doses of RO7239361/placebo weekly. During Part A (first four weeks of Panels 1–3), study drug should be administered every 7 days. During Part B of the double-blind phase (Weeks 5–24 of Panels 1–3 and Expansion Panel) and during the 48-week OL phase, the study drug should be administered every 7 days within a ±1-day window.

Subjects may receive the weekly dose at home, starting on Day 22. If the parent/caregiver has been trained by study site staff and is comfortable administering study drug to the subject, the parent/caregiver will receive an adequate supply of study drug in vial (either RO7239361 or placebo during the double-blind phase and RO7239361 in the OL and OLE phases) and sterile syringes for weekly administration at home to their child in between study visits. The first three weekly doses in the OL phase must be administered at the study site, *as well as the first two PFS doses in the OLE phase*.

In Panels 2 and 3, during the first four weeks of dosing (Days 1–29) the dose of RO7239361 should not be adjusted based on weight. Starting at Week 5, subjects whose weight exceeds or drops below the dosing weight tier to which they were assigned by >1 kg should be assigned to the new weight-based dose in the subject's assigned dose panel.

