5.5.1 Pharmacokinetics: Collection and Processing

Table 5.5.1-1 lists the sampling schedule to be followed for the assessment of pharmacokinetics. Further details of blood collection and processing will be provided to the site in the procedure manual and laboratory manual. A PK test may be repeated if it is determined to be inadequate for analysis.

Table 5.5.1-1: Pharmacokinetic Sampling Schedule for RO7239361

Study Day of Sample Collection	Event	Time of Sample Collection, Relative to Time of Dose Administration	RO7239361 Serum Samples
Day 1, double-blind phase	Predose	00:00	X
Day 1, double-blind phase	Postdose	3:00 ± 15 min	X
Day 1, double-blind phase	Postdose	6:00 ± 15 min	X
Day 4, double-blind phase	Post-Day 1 dose	72:00 ± 8 hours	X
Day 5, double-blind phase	Post-Day 1 dose	96:00 ± 8 hours	X
Day 8, double-blind phase	Predose	00:00	X
Day 15, double-blind phase	Predose	00:00	X
Day 22, double-blind phase	Predose	00:00	X
Day 29, double-blind phase	Predose	00:00	X
Day 33, double-blind phase	Post-Day 29 dose	96:00 ± 8 hours	X
Week 12, double-blind phase	Predose	00:00	X
Week 24, double-blind phase	Predose	00:00	X
Week 1, open-label phase	Predose	00:00	X
Week 12, open-label phase	Predose	00:00	X
Week 24, open-label phase	Predose	00:00	X
Week 36, open-label phase	Predose	00:00	X
Week 48, open-label phase	Predose	00:00	X
*Day 1 after switch to PFS in open-label extension phase	Predose	00:00	X
*Day 8 after switch to PFS in open-label extension phase	Predose	00:00	X
*Day 45 after switch to PFS in open-label extension phase	Postdose	48:00	X

Study Day of Sample Collection	Event	Time of Sample Collection, Relative to Time of Dose Administration	RO7239361 Serum Samples
*Week 12 after switch to PFS in open-label extension phase	Predose	00:00	X
Week 60, open-label extension phase	Predose	00:00	X
Week 84, open-label extension phase	Predose	00:00	X
Week 108, open-label extension phase	Predose	00:00	X
Week 132, open-label extension phase	Predose	00:00	X

Table 5.5.1-1: Pharmacokinetic Sampling Schedule for RO7239361

Study Day of Sample Collection	Event	Time of Sample Collection, Relative to Time of Dose Administration	RO7239361 Serum Samples
Week 156, open-label extension phase	Predose	00:00	X
Week 180, open-label extension phase	Predose	00:00	X
Week 204, open-label extension phase	Predose	00:00	X
Week 228, open-label extension phase	Predose	00:00	X

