8.4.6 Biomarker Analyses

Right thigh CSA_{max}, contractile versus non-contractile content as a key secondary endpoint will be tabulated by dose and study day; and the corresponding changes from baseline and percent change from baseline will be calculated and summarized. Summary and individual profile plots will be provided as appropriate.

A model dose-response (exposure-response) analysis of non-contractile fraction content will be used to characterize the relationship between dose levels (PK parameters) of RO7239361 and changes from baseline in right thigh non-contractile fraction content among 4 muscles in the quadriceps femoris group. This analysis will combine data from Panels 1–3 and the expansion panel.

This model assumes that the change from baseline follows a normal distribution with a mean response that can be expressed in an E_{max} model. If the model results show evidence of heteroscedascity or the E_{max} model does not produce an acceptable fit, then either weighted analyses and/or alternate model specifications may be used. Alternative model specifications may include additional covariates that are relevant to the model.

Similar model-based analyses may be applied for other right thigh muscles/muscle groups CSA_{max} and lipid fraction content.

8.4.7 *Exploratory Biomarker Analyses*

All the exploratory endpoints such as miRNA 206, exploratory blood biomarkers, urinary titin fragments will be summarized.

Subgroup analyses of other primary, secondary, or exploratory endpoints may be conducted based on genetic variation in genes suspected to modify DMD disease expression (including, but not limited to, LTBP4, SPP1). The potential association between genetic variations with certain endpoints from safety, PD, or function test data may be analyzed. Depending on available data, all analyses related to genetic variation in genes may be conducted by pooling data from all RO7239361-treated *subjects* together or by dose/exposure-response modeling.

Summary and individual profile plots will be provided as appropriate.

8.4.8 *Immunogenicity Analysis*

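### The committed dose-proportionality regression has no stated body-weight term, and the committed MRI Emax model has no baseline term

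*Combined protocol and SAP*

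**What the plan says.** **PK.** Section 8.4.4 assesses dose proportionality by a power model: the log of Cmax and of Ctrough is regressed "on the natural log of dose (by tiered body weight", closing the parenthesis there. The synopsis says nearly the same. In Tables 3.1-1 to 3.1-4 the tier determines the mg dose (12.5 or 20 mg in Panel 2; 35 or 50 mg in Panel 3 and the Expansion Panel; 4 mg for all in Panel 1). Section 1.6.4.1, describing the population PK analysis of this trial, states that "body weight was found to be the only covariate", and adds that PK appear dose proportional. Section 8.4.4 allows, but does not require, a population PK/PD model, which may be reported outside the clinical study report.

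From Week 5, under Section 4.5, "subjects whose weight exceeds or drops below the dosing weight tier to which they were assigned" by more than 1 kg move to the other dose of their panel. Table 5.5.1-1 lists the sample labelled "Week 12, double-blind phase", and the Week 24 sample, as predose.

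**MRI.** Section 8.4.6 commits to a dose-response model of non-contractile fraction in the four quadriceps muscles, all panels combined. "This model assumes that the change from baseline follows a normal distribution with a mean response" of Emax form. Other specifications are allowed if variances are unequal or the fit is unacceptable: "Alternative model specifications may include additional covariates that are relevant to the model". No covariate is named.

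For CSAmax and contractile content, Section 8.3.2 defines the endpoint "during the 24-week double-blind treatment period, compared to placebo". Section 8.4.6 says it "as a key secondary endpoint will be tabulated by dose and study day", with plots as appropriate. The synopsis and Section 8.4.6 leave dose-response modelling of these measures optional.

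**The concern.** The one dose-proportionality analysis that the protocol commits to omits the one covariate that the trial's own data identified. Unexplained weight variation goes into the residual and widens the slope interval. Because tiers give heavier boys the larger dose, dose and weight are also positively correlated. If concentration per mg falls with weight, the unadjusted slope is pulled slightly below its true value.

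In the MRI model, boys start with different muscle content, panels are small, and placebo is pooled. A change score without a baseline term carries part of any chance baseline difference into the dose-response. Leaving covariates to be chosen after a poor fit also means that adjustment would be decided with the fit in view.

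Both variables are already collected: weight at screening, Day 1, Day 29, Week 12 and Week 24; thigh MRI before randomization. At stake is the quality of two secondary, descriptive estimates.

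**Working it through.** **The plan's own figure.** Section 8.1 gives 80% probability of at least one adverse event of 24% incidence among 6 treated boys: 1 − 0.76^6 = 0.807. It reproduces and depends on neither model. The plan states no precision target for either model.

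**Numbers of boys.** Randomization 3:1 in panels of 8, 8, 8 and 16 gives 6 + 6 + 6 + 12 = 30 active and 10 pooled placebo. Panel 3 and the Expansion Panel share doses, so the active groups are 6, 6 and 18. With one value per boy, residual degrees of freedom go from 28 to 27 (power model) and from 37 to 36 (three-parameter Emax). That alone widens a 95% interval by 0.17% and 0.09%.

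**PK: a hand check.** Assume ln PK = ln dose − θ·ln weight + error. The documents give no θ, weight spread or residual SD. Central assumption: median 30 kg, weight log-SD s = 0.30, residual SD σ = 0.30. Ignoring the small dose-weight correlation, the unadjusted residual SD is √(σ² + θ²s²):

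- θ = 0.5: √(0.0900 + 0.0225) = 0.335; 0.300/0.335 = 0.89
- θ = 0.75: √(0.0900 + 0.0506) = 0.375; 0.300/0.375 = 0.80
- θ = 1.0: √(0.0900 + 0.0900) = 0.424; 0.300/0.424 = 0.71

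Multiplying by about 1.02, for collinearity and the lost degree of freedom, predicts intervals about 9%, 18% and 28% narrower.

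**PK: simulation.** 4,000 trials per setting, weights lognormal clipped to 15–70 kg, doses from the protocol tables, true slope 1. Central case, mean width of the 90% slope interval:

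| θ | without ln(weight) | with ln(weight) | change |
|---|---|---|---|
| 0 | 0.211 | 0.215 | 2% wider |
| 0.25 | 0.216 | 0.215 | 0.5% narrower |
| 0.5 | 0.235 | 0.216 | 8% narrower |
| 0.75 | 0.261 | 0.215 | 18% narrower |
| 1.0 | 0.296 | 0.216 | 27% narrower |

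Across medians of 25–35 kg, weight log-SD 0.20–0.35 and residual SD 0.2–0.4, the range is 2–3% wider at θ = 0, 1–22% narrower at 0.5 and 9–48% narrower at 1.0. The mean unadjusted slope stays within 0.963–1.002 and coverage of the 90% interval within 0.86–0.91; adjusted, 0.996–1.004 and 0.89–0.91. The downward pull needs boys above 45 kg; these weight assumptions imply about 0.2% (25 kg, 0.20), 9% (central) and 24% (35 kg, 0.35).

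**MRI.** With equal variances before and after and correlation ρ, a change score has variance 2σ²(1 − ρ), and the baseline-adjusted residual has σ²(1 − ρ²). The ratio is (1 + ρ)/2. For two groups totalling N, estimating the slope multiplies this by 1 + 1/(N − 4). For 10 v 18, N = 28 and the factor is 25/24 = 1.042:

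- ρ = 0.9: 0.95 × 1.042 = 0.99
- ρ = 0.7: 0.85 × 1.042 = 0.89
- ρ = 0.5: 0.75 × 1.042 = 0.78

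In simulated Emax fits (10, 6, 6 and 18 boys at 0, 4, 12.5 and 35 mg), the variance of the fitted top-dose effect changes by about +0.2% to +0.5% at ρ = 0.95, −12% to −15% at 0.7 and −22% to −26% at 0.5. At 0.9 the change is at most about 3%.

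**Chance imbalance.** The SD of a baseline mean difference, in baseline SDs, is √(1/10 + 1/6) = 0.516 for 10 v 6 and √(1/10 + 1/18) = 0.394 for 10 v 18. A difference above 0.5 SD therefore occurs 33% and 20% of the time. A 0.5 SD difference shifts the unadjusted change contrast by (1 − ρ) × 0.5, that is 0.05 SD at ρ = 0.9 and 0.25 SD at ρ = 0.5.

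**The case against.** The best defence is that weight has already been dealt with: a population model of this trial's data includes it and found approximate proportionality, so the power model is a simple companion. That lowers the stakes. It does not mend the committed analysis, because the population model is optional and may be reported elsewhere.

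The parenthesis in Section 8.4.4 is loose and could mean fitting by tier. That too calls for clearer wording. The SAP mentioned in Section 8.4.8 may name both terms; this cannot be checked.

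Three further limits stand. The size of the gain rests on assumed inputs and vanishes if weight matters little or ρ is near 0.95. The cost of one degree of freedom assumes one common baseline slope; separate slopes for four muscles would cost four. The MRI simulation used one value per boy and nominal dose, whereas the plan also allows PK parameters as the predictor.

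A reader might infer more than the documents support:

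- *That CSAmax and the contractile ratio get tabulation only.* The commitment is to tabulation and plots, but modelling is allowed as an option.
- *That re-tiering corrupts the PK regression.* Section 4.5 bars weight-based changes on Days 1–29, Panel 1 has no tiers, and administered doses are recorded. Only Week 12 and Week 24 troughs of boys crossing the 45 kg boundary are open to mislabelling, by 20/12.5 = 1.60 or 50/35 = 1.43 if the new dose were attached before it was given.
- *That a baseline term would make sequential panels comparable.* Dose was not randomized across panels. The term handles chance imbalance in the baseline measure and cannot be assumed to remove systematic differences.

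**Conclusion.** The point holds as a modest improvement to two descriptive secondary analyses, limited to protocol Section 8. Both omissions are on the page, and the missing variables are already measured. The gain is mainly precision: about 8% to 27% off the slope interval for weight exponents 0.5 to 1.0 in the assumed central case, and about 11% to 26% off the MRI variance at correlations of 0.7 to 0.5. The slope bias is small and requires an appreciable share of boys above 45 kg, which the documents do not give.

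It would be wrong to conclude that the dose-proportionality finding is unsound. The lowest mean unadjusted slope in any setting examined was 0.963, and the interim population analysis accounted for weight. No formal test, power statement or primary safety conclusion is affected.

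**What to change.** **Section 8.4.4.** Add ln(body weight) as a fixed covariate in the power model, using the latest weight at or before the sample. Define dose as the mg dose actually received before the sample; for a predose trough, this is the last dose given before the draw. State that the tier identifies the dose, if that is what the parenthesis means.

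**Section 8.4.6.** Include the baseline MRI value in the primary Emax model from the outset, with one common slope, or state that slopes differ by muscle and accept the extra degrees of freedom.

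**Both.** Keep the unadjusted fits as sensitivity analyses. Date the change relative to the interim PK results and to any interim MRI data already seen; Section 8.5 allows biomarker data at the second and third interim analyses, and the documents do not say whether MRI data were reviewed.

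**Optional.** For CSAmax and the contractile ratio, report a baseline-adjusted Week 24 difference from pooled placebo by dose level, with a 95% confidence interval and no formal test. This is an added analysis.

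**Cost.** The main change needs wording and no new data. The price is a slope interval 2% to 3% wider if weight has no effect, and no benefit from the baseline term if ρ is near 0.95. If the SAP already names these terms, Section 8 need only be brought into line.
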